2. TRIAL OBJECTIVES AND ENDPOINTS

2.1 MAIN OBJECTIVES, PRIMARY AND SECONDARY ENDPOINTS

2.1.1 Main objectives

The main objective of this trial is to evaluate the photosensitivity potential of BI 730357. All endpoints are applicable for both treatment parts.

2.1.2 Primary endpoint(s)

The primary endpoints are:

- Phototoxicity index at 24 h under condition 1
- Phototoxicity index at 24 h under condition 2

Where condition 1 is full range solar UVB/UVA exposures and Condition 2 is UVA exposure only. Refer to Section 5.1 for the details of photosensitivity assessments and these conditions.

Refer to Section 7.2.2 for the endpoint definitions

2.1.3 Secondary endpoint(s)

- Phototoxicity index at 10 min under condition 1
- Phototoxicity index at 1 h under condition 1
- Phototoxicity index at 10 min under condition 2
- Phototoxicity index at 1 h under condition 2
- MED percent change from baseline at 10min, 1h, and 24h measured under condition 1 and condition 2

Where conditions 1 and 2 are described above in Section 2.1.2.

Refer to Section 7.2.3 for the endpoint definitions.

[figure not shown]

BI Trial No.: 1407-0037

c27983101-03 Clinical Trial Protocol Page 29 of 79

c27983101-03 Clinical Trial Protocol Page 30 of 79

c27983101-03 Clinical Trial Protocol Page 31 of 79

Proprietary confidential information © 2020 Boehringer Ingelheim International GmbH or one or more of its affiliated companies

3. DESCRIPTION OF DESIGN AND TRIAL POPULATION

3.1 OVERALL TRIAL DESIGN

The trial will be performed as partially-blind, randomized, parallel group, placebo and active comparator controlled Phase I clinical trial in healthy male and female subjects aged ≥18 to ≤55 years in order to evaluate the photosensitivity potential of BI 730357 compared to placebo and active comparator, and to assess the relationship between the photosensitivity response and pharmacokinetics of the BI 730357. The subjects will be randomized to one of the two treatments parts (Treatment Part A or Treatment Part B).

In total, approximately 84 healthy male and female subjects (36 subjects each dose group in Treatment A; 12 subjects in Treatment B) are planned to be randomized in this trial to allow for at least 74 completed subjects.

Treatment A will be conducted according to a randomized, double blind, placebo-controlled design to assess the photosensitivity potential, safety and tolerability, and pharmacokinetics of multiple doses of BI 730357. Subjects will be randomized in a 3:1 manner to receive BI 730357 or placebo.

Subjects will receive 400mg of BI 730357 or placebo once daily over 8 days, or 300 mg of BI 730357 or placebo twice daily over 7 days with a single dose on day 8, in order to reach pharmacokinetic steady state;

Light exposure will occur 2 hours (+/-10 min) after the last dose of either IP or placebo, and on-treatment photosensitivity assessments (determination of MED_{On drug} and evaluation of erythema/local skin reactions) will be performed at 10 minutes, and 1, 24, 48, and 72 hours after irradiation.

Treatment B will be conducted according to an open-label, observer-blinded design to assess the photosensitivity potential of ciprofloxacin (a mild photosensitizer) as a positive control.

Subjects will receive 500 mg ciprofloxacin starting on the morning of Day 3. Twelve (12) hours later, subjects received their second dose of 500 mg ciprofloxacin. Subjects continued a twice-daily dosing regimen through to the morning of Day 8 to ensure they reached pharmacokinetic steady state.

Light exposure will occur on Day 8 at 2 hours (+/-10 min) post-dose, and on-treatment photosensitivity assessments (determination of MED_{On drug} and evaluation of erythema/local skin reactions) were performed at 10 minutes, and 1, 24, 48, and 72 hours after irradiation.

This trial will have a screening period of up to 28 days including preliminary photosensitivity assessment on Day -3. Eligible subjects will undergo base line photosensitivity assessment starting after irradiation on day -2 10 min, 1h, 24 hours after irradiation, and will be admitted to the clinical site on Day -1.

c27983101-03 Clinical Trial Protocol Page 32 of 79

Proprietary confidential information © 2020 Boehringer Ingelheim International GmbH or one or more of its affiliated companies

Subjects confirmed eligible will be dosed on Day 1 and be resident until the Day 11. All subjects will remain in the clinic until day 11. The subject will then return to the clinic for ambulatory visit approx. 7 days after the last drug administration for safety follow up (e.o.t.).

Additionally, all AEs, regardless of relatedness, will be collected until 7 days after the administration of trial medication. Adverse events not fully resolved at the End of Trial visit will be followed until recovery or in case of persistency, sufficient characterization has been achieved and the investigator and medical monitor agree to not pursue them further.

For details for treatments to be administered refer to Section 4.1.

An overview of all relevant trial activities is provided in Flow Chart. For visit schedule and details of trial procedures at selected visits, refer to Section 6.1 and Section 6.2, respectively.

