(WoCBP). Human exposures up to those achieved at the no observed adverse effect level (NOAEL) of 5 mg/kg/day in the 4- and 13- weeks dog studies (C_{max} 6,660 nM, and AUC_{0-24} 127,400 nM•h in males and females combined) are considered safe for dosing up to 13 weeks in clinical trials. For clinical trials that exceed 13 weeks duration, human exposures up to those achieved at the NOAEL of 1 mg/kg/day in the 39-weeks dog study (C_{max} 1210 nM, and AUC_{0-24} 22,100 nM•h in males and females combined) are considered safe.

The nonclinical safety package supports long-term administration of BI 730357 to human subjects, including WoCBP.

Data from clinical trials

Two clinical trials have been performed in healthy volunteers.

66 male adult subjects receiving BI 730357 in the Single Rising Dose study 1407.1.

Safety evaluations included physical examination, vital signs, ECG, laboratory tests, and adverse events (AEs). AEs, which generally reflected commonly-occurring events of short duration, and were mostly mild or moderate in severity, were distributed without discernible trend among recipients of placebo and rising dose levels of BI 730357. No serious AEs (SAEs) were reported.

Phase Ib trial 1407-0002 evaluated MRD of BI 730357 ranging from 25 mg to 400 mg, administered as film-coated tablets to healthy male adult subjects aged 18 to 45 years.

83 subjects entered into the trial; each group of 12 subjects was randomized (9 active: 3 placebo) into one of 4 sequential dose groups under fasting conditions (25 mg, 50 mg, 100 mg, 200 mg), and into one of 3 sequential dose groups under fed conditions (50 mg, 200 mg, and 400 mg). Comparison of the mean BI 730357 plasma concentrations indicated that exposure was related to dose, such that exposures increased with increasing dose. When BI 730357 was administered to subjects in the fed state, higher

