BI 730357 plasma levels and exposures were observed, with a delayed peak in concentrations compared to fasted conditions. Median t_{max} values ranged from 1.00 to 2.75 h in the fasted state and increased to 2.55 to 4.00 h in the fed state. Concentrations following multiple dosing appeared to be approximately double those following a single dose, with no relevant difference seen between 2 and 4 week profiles. Subjects were evaluated for safety (physical examination, ECG and laboratory studies, AEs, and SAEs) and PK during once daily study drug treatment for 14 days (dose groups up to 100 mg) or 28 days (200 mg and 400 mg dose groups), and for approximately one week after completion of treatment. Safety data indicate that with respect to the kind, incidence and severity of the AEs, there were no notable differences among dose groups. The most frequently reported AEs were headache in 26.5% and diarrhea in 10.8% of subjects, of subjects across BI 730357 dose groups. No SAEs were reported during the trial. ECG recordings, clinical laboratory evaluation, and vital signs showed no clinically-relevant changes compared to baseline. Overall, administration of BI 730357 to healthy male subjects at doses up to 400 mg for up to 28 days was well tolerated.

c27983101-03 Clinical Trial Protocol Page 20 of 79

Proprietary confidential information © 2020 Boehringer Ingelheim International GmbH or one or more of its affiliated companies

A phase II trial (1407-0030) in patients with moderate-to-severe chronic plaque psoriasis is ongoing, 178 patients were included and randomized in a blinded manne to receive 25 mg, 50 mg, 100 mg, or 200 mg of BI 730357, or placebo, *q.d.*, under fasted conditions, for 24 weeks. Primary analysis data from trial 1407-0030 demonstrate that PsO patients had higher exposure (up to 2.1 fold) compared to those of healthy volunteers in 1407-0002. Moreover, the exposures in PsO patients appear to be increasing with increasing dose, up to the highest (200 mg) dose evaluated, in a close to dose-proportional manner.

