Administration of BI 730357 to patients with moderate-to-severe plaque PsO at doses up to 200 mg for at least 12 weeks has been well tolerated. Through Week 12, the overall frequency of patients with at least 1 treatment emergent adverse events (TEAE) was 50.6% for patients receiving BI 730357 (range 47.5% to 53.8%, vs. 55.0% of placebo recipients). The most commonly reported AEs, by preferred term, were "upper respiratory tract infection" (10.1%, range 2.5% to 15.4%, vs. 15.0% among placebo recipients), "nasopharyngitis" (6.3%, range 5.0% to 7.7%, vs. 0% among placebo recipients), and "headache" (3.2%, range 0% to 5.1%, vs. 0% among placebo recipients). ECG recordings, laboratories, and vital signs showed no clinically-relevant changes compared to baseline.

The non-clinical BI 730357 safety data together with the safety data from the two trials in healthy volunteers (HV) and patients in plaque psoriasis demonstrated an acceptable profile to support clinical trials in males and females, including WoCBP. These data justify the oral dose of 400 mg BI 730357, taken once daily and 300 mg BI 730357 taken twice daily, over 8 days in healthy male and female volunteers. It is anticipated that higher mean BI 730357 exposures as expected with 300 mg dosed b.i.d. under fed conditions for 8 days will not exceed the NOAEL thresholds observed in 13 weeks general toxicity studies.

For a more detailed description of the profile of BI 730357 please refer to the current Investigator's Brochure (IB) (c09228382).

Ciprofloxacin

CIPRO is a fluoroquinolone antibacterial indicated to treat or prevent infections that are proven or strongly suspected to be caused by bacteria.

The absolute bioavailability of ciprofloxacin when given as an oral tablet is approximately 70% with no substantial loss by first pass metabolism.

Maximum serum concentrations are attained 1 to 2 hours after oral dosing. Steady-state C_{max} and AUC of Ciprofloxacin following administration of multiple oral doses to healthy subjects are 2.97 and 13.7 mcg•hr/mL respectively. When CIPRO Tablet is given concomitantly with food, there is a delay in the absorption of the drug, resulting in peak concentrations that occur closer to 2 hours after dosing rather than 1 hour.

For a more detailed description of the profile of Ciprofloxacin please refer to the ciprofloxacin hydrochloride tablet U.S. prescribing information (R19-2246 and R19-3127).

c27983101-03 Clinical Trial Protocol Page 21 of 79

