As with other immune-targeted therapies, impaired host defence is a theoretical target-related toxicity, potentially resulting in increased risk of infection and/or malignancy. Subjects with latent TB infection or TB disease, also subjects with HBV, HCV, HIV or any other clinically relevant bacterial or fungal infections will be excluded at screening.

Risk to subjects will also be minimized in this trial by implementing conservative eligibility criteria.

Homozygous, but not heterozygous RORC knockout mice have a high incidence of T cell lymphoma, thought to originate in the Thymus. While the translatability of the knockout phenotype to pharmacological RORγ antagonism and to humans is unknown, this raises the hypothetical concern for clinical T cell lymphoma risk. The exact cause of T cell lymphomas in RORC knockout mice is not fully understood, but changes in homeostasis in the thymus, such as thymocyte apoptosis and proliferation, are thought to play a role. AEs and SAEs consistent with malignancy, and specifically those representing lymphoma, will be carefully monitored and evaluated as well as monitoring of peripheral blood lymphocyte subsets will be integrated into this clinical trial.

An *in vivo* phototoxicity study in rats was conducted in pigmented rats. No cutaneous reactions indicative of phototoxic response were seen at 10 mg/kg/day, which corresponded to mean C_{max} and AUC_{0-24} values of 4,520 nM and 35,200 nM•h, respectively. No ophthalmic changes indicative of phototoxicity were seen up to 30 mg/kg/day, which corresponded to a mean C_{max} and AUC_{0-24} values of 13,500 nM and 107,000 nM•h, respectively.

Dose 400 mg BI 730357 planned to be tested in this study was administered once daily over a period of 4 weeks in the MRD study 1407-0002. The pharmacokinetic parameters observed in this study - AUC_{0-24} [nmol*h/L] 15,600 ($AUC_{\tau,ss}$ [nmol*h/L] 35,500) and C_{max} [nmol/L] 1320 ($C_{max,ss}$ [nmol/L] 2210) indicate that the plasma concentrations and exposures, which might be achieved in this study, are lower than those observed in *in vivo* phototoxicity study in rat where the phototoxic responses have been seen.

c27983101-03 Clinical Trial Protocol Page 23 of 79

Proprietary confidential information © 2020 Boehringer Ingelheim International GmbH or one or more of its affiliated companies

Ciprofloxacin

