4.1.4 Drug assignment and administration of doses for each patient

The trial medication will be administered to the subjects as an oral dose together with about 240 mL of water under supervision of the investigating physician or an authorised designee. To ensure a dosing interval of 24 and 12 hours for treatment group Part A and 12 hours in treatment Part B, the administration of trial medication should take place at the same time every day within a deviation of no more than +/-15 min. A standard continental breakfast (table 4.1.4:1) should be taken after blood sampling and before the study drug administration (the safety laboratory samples will be taken as the first morning sample from all subjects after at least 6 hours fast prior). The consumption of the continental breakfast will occur within 30 minutes prior to dosing and can occur as for Days 2 -Days 8 before PK samples are collected. A light morning snack can be consumed in the mornings if dosing occurs after 11 am. Further, subjects will consume a snack within 30 minutes prior to their evening dosing.

The medication phase will be followed by a 7 day follow-up and wash-out period.

Table 4.1.4: 1 Composition of the standard continental breakfast as an example

Ingredients	kcal
1 bread roll	164
15 g butter	113
1 slice of Gouda cheese (approximately 40g)	146
1 slice of meat (approximately 20g)	33
1 cup of decaffeinated coffee or tea (without sugar)	2
Sum ¹	458

The total caloric content is supplied approximately as following: approx. 88 kcal as protein, approx. 133 kcal as carbohydrate, and approx. 237 kcal as fat.

01 Apr 2020

c27983101-03 Clinical Trial Protocol Page 41 of 79

Proprietary confidential information © 2020 Boehringer Ingelheim International GmbH or one or more of its affiliated companies

Table 4.1.4: 2 BI 730357, placebo and ciprofloxacin treatments

Treat ment group	Fasting condition predose	Substance	Pharmaceutical form	Unit strength	Number of units /dose volume per administration	Total dose
A	Fed ¹	BI 730357	Film-coated tablet	100 mg	4 tablets QD	400 mg
A	Fed ¹	Placebo	Film-coated tablet		4 tablets QD	
В	Fed ¹	Ciprofloxacin	Film-coated tablet	500 mg	1 tablet BID	1000mg
A	Fed ²	BI 730357	Film-coated tablet	100 mg	3 tablets BID	600 mg
A	Fed ¹	Placebo	Film-coated tablet		3 tablets BID	

- 1 Drug administration after a standard continental breakfast
- 2 Drug administration after a standard continental breakfast and evening snack

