01 Apr 2020

BI Trial No.: 1407-0037

c27983101-03 Clinical Trial Protocol Page 46 of 79

Proprietary confidential information © 2020 Boehringer Ingelheim International GmbH or one or more of its affiliated companies

Day -2

- Assessment of Preliminary MEDs at at 24 hours ± 10 minutes post irradiation.
- Irradiate Baseline MEDs (Condition 1 and Condition 2, \pm 30 min to planned time) followed by MED assessments at 10 \pm 2 minutes, 1 hour \pm 5 minutes

Day -1

- Assessment of Baseline MEDs (Condition 1 and Condition 2) at 24 hour±10 minutes post irradiation.
- Irradiate Baseline Condition 3 (\pm 30 min to planned time) followed by assessments at 10 \pm 2 minutes and 1-hour \pm 5 minutes.

Day 1

Post-treatment photosensitivity testing will occur 2 hours (± 10 minutes) after final dose administration on day 8, with the same irradiation conditions as on day -1 as follows:

Day 8

- Irradiate MEDs (Condition 1 and Condition 2) followed by MED assessments at 10 ±2 minutes, 1 hour ±5 minutes
- Irradiate Condition 3 followed by assessments at 10 ± 2 minutes, 1 hour ± 5 minutes

Day 9

• Assessment of MEDs (Condition 1 and Condition 2) at 24 hour±10 minutes post irradiation.

• Assessment of Condition 3 at 24 hours post hours ± 10 minutes post irradiation.

The photosensitivity index (PI) will be calculated as the ratio of the MED_{baseline} versus MED_{on drug} for irradiation Conditions 1 and Conditions 2.

Additionally, inflammatory responses (erythema and local skin reactions) and superficial skin effects will be scored (see scales in Table below) under all conditions at baseline (10 min, 1 h and 24 h post-irradiation), and post-treatment day 8 (10 min, 1 h, 24 h, 48 h and 72 h post-irradiation).

c27983101-03 Clinical Trial Protocol Page 47 of 79

Proprietary confidential information © 2020 Boehringer Ingelheim International GmbH or one or more of its affiliated companies

Inflammatory skin reactions will be scored according to:

Skin Reaction Grading Scales

Erythema Grading Scale	Local Skin Reaction	Superficial Effects Grading
0 No evidence of erythema	E Edema-swelling, spongy feeling when palpated	g Glazing
1 Very slight erythema (barely perceptible)	P Papule-red, solid, elevation	y Peeling
2 Well defined erythema	V Vesicle-small elevation containing fluid	c Scab, dried film of serous exudate of vesicular or bullous reaction

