6.2.2 Treatment period(s)

Treatment A

Subjects will be randomized in the morning on Day 1 and receive 400mg of BI 730357 or placebo once daily over 8 days, or 300mg of BI 730357 or placebo twice daily 12 hours apart over 8 days with the single dose on day 8, in order to reach pharmacokinetic steady state;

UVB/UVA irradiation will occur 2 hours after the last dose of either IP or placebo, and photosensitivity assessments (determination of MED_{On drug} and evaluation of erythema/local skin reactions) will be performed at 10 (+/- 2) minutes, and 1 (+/- 5 min), 24(+/- 10 min)

Treatment B

Subjects will receive their first dose of 500 mg ciprofloxacin on the morning of Day 3. Twelve (12) hours later, subjects received their second dose of 500 mg ciprofloxacin. Subjects continued a twice-daily dosing regimen through to the morning of Day 8 to ensure they have reached pharmacokinetic steady state

UVB/UVA irradiation will occur 2 hours after the last dose of Ciprofloxacin, and photosensitivity assessments (determination of MED_{On drug} and evaluation of erythema/local skin reactions) were performed at 10 (+/- 2) minutes, and 1(+/- 5 min), 24(+/- 10 min),

For details on time points for all other trial procedures, refer to the Flow Chart. AEs and concomitant therapy will be assessed continuously from screening until the end of trial examination.

01 Apr 2020

c27983101-03 Clinical Trial Protocol Page 61 of 79

Proprietary confidential information © 2020 Boehringer Ingelheim International GmbH or one or more of its affiliated companies

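### Part A is dosed fed but irradiated at 2 h, before every fed median tmax reported for BI 730357, while ciprofloxacin is irradiated at about its fed peak; the shortfall is probably modest and cheap to remove

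*Protocol*

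**What the plan says.** Protocol 3.1 sets the time of light for Part A: "Light exposure will occur 2 hours (+/-10 min) after the last dose of either IP or placebo". Section 5.1 repeats it ("Post-treatment photosensitivity testing will occur 2 hours", with a 10-minute window), as does section 6.2.2 ("UVB/UVA irradiation will occur 2 hours after the last dose of either IP or placebo"), and the flow charts put irradiation at 170:00. Part B is also irradiated 2 h after its last dose.

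Dosing is fed. Under Protocol 4.1.4 the breakfast "should be taken after blood sampling and before the study drug administration", and Table 4.1.4:2 lists every arm as fed.

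Protocol 1.2 reports that median tmax of BI 730357 in the multiple-dose trial "ranged from 1.00 to 2.75 h in the fasted state and increased to 2.55 to 4.00 h in the fed state". The fed groups were 50, 200 and 400 mg, once daily. For ciprofloxacin, the same section says that food delays absorption, "resulting in peak concentrations that occur closer to 2 hours after dosing rather than 1 hour".

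SAP 15.4 concludes absence of photosensitivity for a dose cohort when the 90% CI for the BI 730357 minus placebo difference in PI at 24 h lies within (-0.4, 0.4). Both conditions are read from that one irradiation. Protocol 7.1 and SAP 15.4 treat a significant ciprofloxacin result as support for the design. The visible text gives no reason for choosing 2 h and plans no later irradiation.

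**The concern.** The 2 h time fits the fasted peak of BI 730357 and the fed peak of ciprofloxacin. It does not fit the fed peak of BI 730357, although the trial doses fed.

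If the skin reaction follows plasma level within the day, PI is measured while the level is still rising. A limit of 0.40 applied at 2 h then corresponds to a wider limit at peak, and the error runs one way, toward a false clean result. A positive ciprofloxacin result would not expose this, because ciprofloxacin is not tested early.

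The level at the time of light matters for the purpose of the trial. SAP 4.1 says 300 mg BID was added to reach exposures like those of patients on 200 mg BID, and the conclusion is worded for the dose, not for the level present at 2 h.

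**Working it through.** **1. The plan's own figures.** The documents give no calculation for the timing. The powers in Protocol 7.5 reproduce: equivalence above 99.99% (stated 99%), BI 730357 v ciprofloxacin 87.8% (stated 87%), placebo v ciprofloxacin 86.7% (stated 86%). They are not in dispute; their inputs are reused in step 4.

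**2. Timing.** The light window is 2 h ± 10 min, or 1.83 to 2.17 h. Fed median tmax is 2.55 to 4.00 h. The gap from the latest permitted light to the lowest fed median is 2.55 − 2.17 = 0.38 h. From nominal light it is 0.55 to 2.00 h. The 400 mg fed group is one of those behind the range, so for 400 mg QD the comparison is direct. For 300 mg BID no tmax is given.

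**3. How far below peak is the 2 h level?** The within-day profile is not given, so this is a range under assumptions. Inputs for 400 mg are in Protocol 1.4.2, from the regimen that "was administered once daily over a period of 4 weeks in the MRD study 1407-0002": first-dose Cmax 1320, Cmax,ss 2210, AUC0-24 15,600, AUCτ,ss 35,500 (nmol/L and nmol·h/L).

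- The level does vary within the day: average over peak at steady state = 35,500 / 24 / 2210 = 67%.
- Simple superposition, QD: carry-over = 2210 − 1320 = 890. If the dose has reached a share c of its own single-dose peak at 2 h, then share of steady-state peak = (890 + 1320c) / 2210. For c = 0.98, 0.83, 0.69 and 0.54 this gives 0.99, 0.90, 0.81 and 0.73.
- Two-compartment fits to the four values above (matched within 2%), evaluated on Day 8:

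| Assumed absorption | tmax | 400 mg QD | 300 mg BID |
|---|---|---|---|
| First-order, no lag | 2.55 h | 99% | 100% |
| First-order, no lag | 4.00 h | 89% | 96% |
| First-order, 1 h lag | 4.00 h | 79% | 89% |
| Constant-rate | 4.00 h | 70% | 83% |

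- One-compartment runs without lag (half-life 12 to 30 h assumed) give 90 to 99% for QD and 97 to 100% for BID, where the model tmax is 2.1 to 3.2 h.
- Combining constant-rate absorption with a 1 h lag at tmax 4 h gives 57% and 75%. The documents support neither assumption, so I do not rely on that case.
- At 4 h, the share across all the two-compartment fits, lag cases included, is 91 to 100% (QD) and 92 to 100% (BID).

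**4. Effect on the decision.** Assume that excess PI is proportional to plasma level. Limit at peak = 0.40 / share: 0.40/0.89 = 0.45, 0.40/0.83 = 0.48, 0.40/0.79 = 0.51, 0.40/0.70 = 0.57.

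Next, the chance that a true excess of 0.40 at peak passes one condition, with 27 v 9 subjects, SD 0.15 and ciprofloxacin SD 0.6 with n = 12 (Protocol 7.5). SAP 15.2 fits one covariance to all three arms. With complete data, residual variance at 24 h = (34 × 0.15² + 11 × 0.6²) / 45 = 4.725 / 45 = 0.105, so SD = 0.324. The CI half-width is about 1.679 × 0.324 × √(1/27 + 1/9) = 0.209, so the estimate must typically fall below about 0.19 to pass. Its true standard error is only 0.15 × 0.385 = 0.058. Simulation of 400,000 trials:

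| Share of peak at 2 h | Planned three-arm model | Two arms only, SD 0.15 |
|---|---|---|
| 1.00 | 0.1% | 5% |
| 0.90 | 0.7% | 17% |
| 0.83 | 2% | 31% |
| 0.75 | 6% | – |
| 0.70 | 10% | 65% |

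In the planned model the chance crosses 5% at a share of about 75%.

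**The case against.** Most of the case against concerns size, and much of it stands.

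- **300 mg BID.** A reader might infer that both doses are shown to be tested before their own peak. The documents do not support that: the fed groups were once daily, and twice-daily dosing can bring the steady-state peak close to 2 h.
- **Large shortfalls.** A reader might also take 70% of peak, or a 65% chance of a false pass, as the expected result. The first needs tmax at 4 h plus constant-rate absorption, and Protocol 1.2 does not say which fed dose had the 4.00 h median. The second also needs a two-arm analysis that the SAP does not plan. In the planned model the large ciprofloxacin variance widens the interval and keeps false passes below 5% until the share is about 75%. That protection depends on the ciprofloxacin SD being as large as Protocol 7.5 assumes.
- **Skin persistence.** Protocol 1.2 reports long half-lives of radioactivity in dermal tissue, and the risk table in 1.4.2 gives long dermal persistence as a basis for the phototoxicity risk. Both point away from a skin level that tracks plasma hour by hour. If it does not track, the 2 h time costs nothing. The documents do not show that it is flat within the day.
- **The BID cohort may cover the 400 mg QD peak.** Under dose proportionality (an assumption), average BID level = 35,500 × 1.5 / 24 = 2,219 nmol/L, against Cmax,ss of 2,210 for 400 mg QD. This helps if that cohort is run and passes, but does not address its own peak.
- **The level is measured.** Protocol 10.2 takes a sample at 170:00 and others at 1, 3, 4, 6 and 12 h after the Day 8 dose. But the decision rule does not use them, and Protocol 5.3.1 makes the concentration–response analysis optional.
- **The remedy.** 4 h is the top of the tmax range and could be slightly past the peak, and one ciprofloxacin group serves both cohorts. The first costs at most about 9% of peak in the fits. The second is not a bar: PI is a within-subject ratio, and each drug would be irradiated near its own peak.

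**Conclusion.** The timing mismatch is in the documents: fed dosing, light at 2 h, every reported fed median tmax of BI 730357 later than the light window, and ciprofloxacin irradiated at about its peak. It is established for 400 mg QD and extrapolated for 300 mg BID.

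The shortfall is probably modest: about 89 to 100% of peak for QD and 96 to 100% for BID with no-lag first-order absorption, reaching about 70% and 83% only under assumed constant-rate absorption with tmax 4 h. The planned model's chance of passing a true peak excess of 0.40 for one condition exceeds 5% only at a share of about 75% or lower. All of this assumes that PI excess is proportional to plasma level; if skin level is steady within the day, the loss is zero.

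A reader might infer that the trial cannot support a conclusion of no photosensitivity. The documents do not support that reading. The conclusion should refer to the level actually present at irradiation, and the timing is worth correcting because doing so is cheap.

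**What to change.** 1. For any Part A cohort not yet irradiated, move light into the fed tmax range, 3 to 4 h (± 10 min) after the Day 8 dose, in Protocol 3.1, 5.1, 6.2.2 and the flow charts. Four hours is the most robust choice, at about 91% of peak or more in every profile tried. The existing 171:00 or 172:00 PK sample then gives the level at irradiation. Keep the readings at 10 min, 1, 24, 48 and 72 h after light.
2. Keep ciprofloxacin light at 2 h after its dose. If Part B runs alongside Part A, delay its clock dosing time by the same 1 to 2 h, so that both parts are irradiated together and the observer stays blinded. Otherwise leave it.
3. For any cohort already irradiated at 2 h, report each subject's 170:00 concentration as a share of Day 8 Cmax beside PI, and state the absence-of-photosensitivity conclusion for that level.

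Cost: Part A readings, and discharge on Day 11, move 1 to 2 h later. There is no new visit, sample or subject, and PI, the model, the limits and the sample size are unchanged. If 400 mg QD has already been run at 2 h, the two dose groups will differ in light timing while sharing one ciprofloxacin control. They are analysed separately, but the difference should be stated in the report.
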